10.4.7 Planned Interim Analysis

Not applicable.

10.4.7.1 Safety Review

Not applicable.

10.4.7.2 Efficacy Review

Not applicable.

10.4.8 Additional Sub-Group Analyses

To obtain a robust estimate of the treatment effect, we will perform secondary analyses within a per-protocol (PP) sample, defined in the Sleep Intervention arm as obtaining at least 1 hour/night longer in

CONFIDENTIAL

This material is the property of the NYU School of Medicine and NYU Langone Health. Do not disclose or use except as authorized in writing by the study sponsor

Behavioral Intervention Template Version: 11 January 2019

sleep by the end of the 8-week protocol. Controls that show over a 1 hour/night increase in their habitual sleep durations, such that they meet the above definition for investigational patients, will also be excluded from the PP sample. In our preliminary data utilizing the proposed intervention, 4 of 5 (80%) individuals met this criteria; the remaining participant almost achieved this threshold, with 57.7 minutes increased sleep; thus, we expect at least 80% of the sample to be retained in PP analyses.

Primary or secondary endpoints may be analyzed for descriptive purposes by age, race/ethnicity, or any other participant characteristic as described in detail in the SAP.

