5.7 Participant Withdrawal or Termination

5.7.1 Reasons for Withdrawal or Termination

Participants are free to withdraw from participation in the study at any time upon request. An investigator may terminate participation in the study if:

- Any clinical adverse event (AE), laboratory abnormality, or other medical condition or situation occurs such that continued participation in the study would not be in the best interest of the participant.
- The participant meets an exclusion criterion (either newly developed or not previously recognized) that precludes further study participation.
- At the discretion of the PI for lack of adherence to the intervention or study procedures or visit schedules (e.g., target 80% of weekly daily diary completion and 80% attendance at intervention sessions). Reasons for less adherence will be assessed, and if addressable will be re-evaluated at the next scheduled intervention session.
- The participant does not respond to weekly phone calls/emails for 4 weeks during the intervention.

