5.7.2 Handling of Participant Withdrawals or Termination

Participants will be considered withdrawn if they cannot be contacted for 4 weeks during the intervention using all of the contact information collected. No further efforts will be made to contact the participant and that participant will be considered lost to follow-up. Abrupt termination of participation in the study intervention poses no safety risk to participants. As this study is minimal risk, efforts will not be made to collect safety and efficacy data after withdrawal. If a participant withdraws or is withdrawn from the study, no further study visits or procedures will be completed. It will be documented whether or not each subject completes the clinical study.

CONFIDENTIAL

This material is the property of the NYU School of Medicine and NYU Langone Health. Do not disclose or use except as authorized in writing by the study sponsor
Behavioral Intervention Template Version: 11 January 2019

Any data collected before withdrawal from the study will be retained for analysis, and no new data will be collected. If the participant requests that data be destroyed, all paper records will be shredded, and any data already processed into computer files will be removed. However, if results based on the participant's data have been submitted for publication or presentation before the request is made, the results cannot be removed from the publication or presentation.

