10.4.5 Adherence and Retention Analyses

Intervention compliance will be defined by 80% completion rate of daily sleep diaries and 80% attendance at the intervention sessions.

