10.5 Sample Size

The primary analyses will involve comparing the mean change in the percent time glucose is ≥ 140 from baseline between the sleep intervention and control intervention arms. The study by Leproult et al⁷⁶ (N=16) reported no significant changes in insulin or glucose with sleep extension, but did not provide effect sizes for determining power; they did report large significant correlations ($\rho > 0.6$) between increased sleep time and insulin. Thus, for powering the current study, effect size assumptions come from previous research examining effects of weekend sleep extension on improvement in the calculated area under the glucose curve (Glucose AUC), which is similar to the primary endpoint we are studying here. Specifically, Killick et al⁷⁵ observed a mean improvement in Glucose AUC of 69.2 mmol min.L⁻¹ (SD = 57.7) associated with weekend sleep extension; this corresponds to an effect size of ~1.2 standard deviations. If we observe this large effect, we would need 20 subjects per arm to have 95% power in the current study, at an $\alpha = 0.05$. To protect against over-estimates in this observed effect, which was conducted in a study with <20 individuals and relied on a different sleep intervention than proposed here, we note that 74 individuals per arm would be required to maintain 95% power in the ITT analysis set for a 50% reduction in this effect (i.e., 0.6 SDs) at an alpha of 0.05; thus, we will recruit 75 subjects per arm in the current study. Under our expectation that at least 80% will achieve our PP definition (n=60 per arm), we would maintain power of at least 90% for this effect size in the PP analysis set. To maintain power for up to 20% loss to follow-up or non-adherence during the 8-week intervention, we will plan to enroll a total of 188 participants in the two arms.

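### The secondary per-protocol set selects on post-randomisation sleep gain, in opposite directions by arm, so it cannot be called a robust estimate of the treatment effect

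*Protocol*

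**What the plan says.** Protocol 10.3 and SAP 1.2 make ITT the primary analysis set. Protocol 10.4.8 adds a second set: "To obtain a robust estimate of the treatment effect, we will perform secondary analyses within a per-protocol (PP) sample". In the sleep arm the set is "defined in the Sleep Intervention arm as obtaining at least 1 hour/night longer in" sleep by the end of the eight weeks. In the control arm the rule runs the other way: "Controls that show over a 1 hour/night increase in their habitual sleep durations" are excluded.

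The expected retention comes from pilot data on people who received the intervention, where "4 of 5 (80%) individuals met this criteria". Protocol 10.5 carries this into a power statement: "Under our expectation that at least 80% will achieve our PP definition (n=60 per arm), we would maintain power of at least 90" per cent, for the same 0.6 SD effect used for ITT.

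Protocol 10.4.5 defines compliance separately, by diary completion and session attendance, and the PP set does not use that definition. The supplied SAP text does not mention a PP set. Neither document attaches a caveat about selection to the PP analysis.

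**The concern.** Sleep gain is measured after randomisation. The PP rule cuts off its lower tail in one arm and its upper tail in the other, so the two groups differ by construction in whatever drives sleep gain. If any such driver also moves glucose by a route other than sleep, the PP contrast picks it up as if it were an intervention effect.

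The documents make shared causes plausible. Protocol 10.4.2 justifies its covariates by their association with both sleep and glycaemic control, and names diet quality and physical activity among them. SAP 1.3.2 adjusts only for age, sex and race. Both arms receive nutrition and activity content (Protocol 6.1), so an engaged participant could gain sleep and lower glucose by separate routes.

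A PP benefit could therefore appear with no true effect on glucose. The PP set has its own power statement, so it is evidently meant to be interpreted, and a reader told that it is robust could give it weight it has not earned.

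**Working it through.** **1. The plan's own figures (Protocol 10.5).** Evaluable per arm: 75. PP set: 75 × 0.80 = 60 per arm. At 0.6 SD and two-sided alpha 0.05, the noncentrality is 0.6 × √(60/2) = 3.286. Power is Φ(3.286 − 1.960) = 0.908 by the normal approximation and 0.903 by the noncentral t. The stated value of at least 90% reproduces.

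**2. Model for the bias.** Inputs from the plan: 75 evaluable per arm, 80% of the sleep arm kept, two-sided alpha 0.05. Assumptions: no true glucose effect; sleep gain and fall in glucose bivariate normal within arm; the same r in both arms, where r is the non-causal correlation remaining after covariate adjustment. The share of controls removed is also unknown. I take 0%, 5% and 20%, the last giving the plan's minimum of 60 per arm.

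**3. Formula.** Keeping the top share p of a standard normal raises its mean by φ(z)/p, where z is the cut-off. Keeping the bottom share p lowers it by the same amount. The bias in the PP contrast, in SD of glucose change, is r × (shift in sleep arm + shift in controls).

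- Sleep arm, 80% kept: 0.280/0.80 = 0.350.
- Controls, none removed: 0.
- Controls, 5% removed: 0.103/0.95 = 0.109.
- Controls, 20% removed: 0.280/0.80 = 0.350.

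**4. Type I error.** With δ = bias/SE and SE = √(1/n₁ + 1/n₂), type I error ≈ Φ(−1.96 + δ) + Φ(−1.96 − δ). At an assumed r = 0.2:

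| Controls removed | n kept (sleep / control) | Bias | Bias at r = 0.2 | SE | δ | Type I error |
|---|---|---|---|---|---|---|
| 0% | 60 / 75 | 0.35 × r SD | 0.070 | 0.173 | 0.40 | 6.9% |
| 5% | 60 / 71 | 0.46 × r SD | 0.092 | 0.175 | 0.52 | 8.2% |
| 20% | 60 / 60 | 0.70 × r SD | 0.140 | 0.183 | 0.77 | 12.0% |

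Simulation with a pooled t test (40,000 trials per cell) gives 6.8%, 8.1% and 11.7%.

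**5. Across r.** At r = 0 there is no bias and type I error is 5%. At r = −0.2 the bias is −0.07, −0.09 and −0.14 SD, against the intervention. At r = 0.4 type I error is about 13%, 19% and 35% in the three rows. In the same simulations, ITT on all 75 per arm stays at about 5% throughout.

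**6. Would the compliance rule remove the bias?** Keep the most adherent 80% of each arm. The bias is then 0.350 × (r in sleep arm − r in controls), with r now between adherence and fall in glucose. At an assumed 0.3 against 0.1 it is 0.07 SD; at 0.3 against 0 it is 0.105 SD. It is zero only if retention and correlation both match across arms.

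**The case against.** The strongest reply is that this reaches very little. The analysis is secondary, sits under additional sub-group analyses, and is absent from the supplied SAP. No passage makes a PP result a decision rule or says it will be offered as support for ITT. That stands. The documented fault is one claimed property and a missing caveat.

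The size also rests on an r that no document gives. That stands too, so the figures are a range. The correlation above 0.6 cited in Protocol 10.5 concerns insulin and is not a non-causal correlation with glucose, so it cannot anchor r. A reader might infer a false-positive rate of 20% to 35%. That needs both r of 0.3 to 0.4 and 20% of controls removed. The latter applies to controls a retention floor taken from five treated people, which says nothing about how many controls would gain over an hour on generic sleep advice.

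The PP set does address the contrast of improved with habitual sleep in Protocol 10.4.1. True, but aiming at that contrast does not remove the confounding in it.

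A reader might also conclude that the set should be rebuilt on the compliance rule: "Intervention compliance will be defined by 80% completion rate of daily sleep diaries and 80% attendance at the intervention sessions". The documents do not support that as a correction. It measures adherence rather than sleep gain, so it drops the stated contrast. It may nearly coincide with the retained sample, because section 5.7.1 lets the PI end participation against the same thresholds ("target 80% of weekly daily diary completion and 80% attendance at intervention sessions") and section 5.7.2 says "efforts will not be made to collect safety and efficacy data after withdrawal". The arms adhere to different content, so equal correlations cannot be presumed. The SAP is written in the past tense, which suggests that analysis has taken place; a new definition could then be post hoc.

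**Conclusion.** The point holds as a fault of description and interpretation. Selecting on sleep gain in opposite directions by arm removes the protection of randomisation, and nothing elsewhere in the documents restores it, so the claim of robustness is not justified. That conclusion does not depend on r; only the size does. Under the stated model the bias is 0.35 to 0.70 × r SD as the share of controls removed goes from none to 20%, with type I error of about 7% to 12% at an assumed r of 0.2.

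Three stronger readings fail. The trial's main result is not undermined: the ITT analysis and N=188 do not depend on this set. The PP power statement is not miscalculated, although it presumes an unbiased 0.6 SD contrast. The bias need not favour the intervention, because its direction follows the sign of r. The 80% retention figure, from 4 of 5 people (exact 95% interval 28% to 99%), is a caveat and not an error.

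**What to change.** In Protocol 10.4.8, delete the word describing the estimate as robust. Describe the sleep-gain contrast as exploratory, subject to selection bias because it conditions on a post-randomisation outcome, and not as confirmation of the ITT result. Report the number excluded in each arm, with reasons.

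If a PP result is to be reported, put the same definition and label in the SAP. Keep the pre-specified PP definition. An additional analysis by the section 10.4.5 compliance rule is optional; it should carry its own caveat about selection and be marked post hoc if outcomes have been seen.

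The cost is a few sentences in the protocol and, if needed, a short SAP paragraph, with no new data. The downside is that the PP result carries less weight.

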10.4.9 Multiple Comparison/Multiplicity

Not applicable.

10.4.10 Tabulation of Individual Response Data

For these analyses, the investigators will generally not control for multiple comparisons.

10.4.11 Exploratory Analyses

The same analytic approach described in Section 10.4.2 will be used to assess the effect of the sleep intervention with the subject specific change in diet quality and physical activity.

10.5 Sample Size

The primary analyses will involve comparing the mean change in the percent time glucose is ≥ 140 from baseline between the sleep intervention and control intervention arms. The study by Leproult et al⁷⁶ (N=16) reported no significant changes in insulin or glucose with sleep extension, but did not provide effect sizes for determining power; they did report large significant correlations ($\rho > 0.6$) between increased sleep time and insulin. Thus, for powering the current study, effect size assumptions come from previous research examining effects of weekend sleep extension on improvement in the calculated area under the glucose curve (Glucose AUC), which is similar to the primary endpoint we are studying here. Specifically, Killick et al⁷⁵ observed a mean improvement in Glucose AUC of 69.2 mmol min.L⁻¹ (SD = 57.7) associated with weekend sleep extension; this corresponds to an effect size of ~1.2 standard deviations. If we observe this large effect, we would need 20 subjects per arm to have 95% power in the current study, at an $\alpha = 0.05$. To protect against over-estimates in this observed effect, which was conducted in a study with <20 individuals and relied on a different sleep intervention than proposed here, we note that 74 individuals per arm would be required to maintain 95% power in the ITT analysis set for a 50% reduction in this effect (i.e., 0.6 SDs) at an alpha of 0.05; thus, we will recruit 75 subjects per arm in the current study. Under our expectation that at least 80% will achieve our PP definition (n=60 per arm), we would maintain power of at least 90% for this effect size in the PP analysis set. To maintain power for up to 20% loss to follow-up or non-adherence during the 8-week intervention, we will plan to enroll a total of 188 participants in the two arms.

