10.3 Analysis Datasets

Primary analyses will be performed within an intent-to-treat (ITT) sample, including all participants that are randomized to either the Sleep Intervention or Control Intervention.

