## **1.2 Analysis Datasets**

Primary analyses were performed within an intent-to-treat (ITT) sample, including all participants that were randomized to either the Sleep Intervention or Control Intervention.

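### Does enrolling 188 keep 95% power under 20% non-adherence when the primary analysis is intent-to-treat?

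*Protocol*

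**What the plan says.** Protocol 10.5 halves a published effect of about 1.2 SD to 0.6 SD because the source study was "conducted in a study with <20 individuals and relied on a different sleep intervention than proposed here". At 0.6 SD it finds that "74 individuals per arm would be required to maintain 95% power in the ITT analysis set" and sets 75 per arm. For the per-protocol (PP) set of 60 per arm it says "we would maintain power of at least 90% for this effect size in the PP analysis set". It then raises the total to 188 "To maintain power for up to 20% loss to follow-up or non-adherence during the 8-week intervention". The Schematic of Study Design shows the same step as 94 per arm enrolled to keep 75.

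The primary set is intent-to-treat in both documents: "including all participants that are randomized to either the Sleep Intervention or Control Intervention" (Protocol 10.3) and "including all participants that were randomized to either the Sleep Intervention or Control Intervention" (SAP 1.2).

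Protocol 10.4.5 defines compliance as 80% of sleep diaries and 80% of sessions. Protocol 5.7.1 allows withdrawal "At the discretion of the PI for lack of adherence to the intervention or study procedures or visit schedules", with the same two 80% targets as examples. After withdrawal, "efforts will not be made to collect safety and efficacy data after withdrawal" (Protocol 5.7.2).

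**The concern.** Loss to follow-up and non-adherence affect an intent-to-treat comparison differently. A lost participant removes an outcome, and enrolling more people replaces it. A non-adherent participant who is measured stays in the analysis and may pull the sleep arm's mean towards the control mean. Dividing by 0.8 restores a count, not a diluted effect.

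Such participants can exist. Someone who attends 6 of 8 sessions (75%) misses the compliance target, and withdrawal for this is discretionary, so that person may still wear the glucose monitor at the end of treatment.

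If 0.6 SD were the effect in adherent participants, the claim of 95% power under 20% non-adherence would be too strong, and a report that repeated it would overstate what the trial could detect.

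**Working it through.** **Inputs.** Two-sided alpha 0.05 (10.5 and 10.4.2); equal arms; effects of 1.2 and 0.6 SD, 75 and 60 per arm, and the 20% allowance (10.5); 94 per arm (Schematic). The share r of the effect kept by measured non-adherers is in neither document. It is an assumption here, shown as a range.

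**Method.** Two-sample t test with n per arm and standardised difference d. Power comes from the noncentral t distribution with 2n − 2 degrees of freedom and noncentrality d × √(n/2).

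**1. The plan's own figures.**

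| n per arm | d | Noncentrality | Power | Plan states |
|---|---|---|---|---|
| 20 | 1.2 | 1.2 × √10 = 3.79 | 95.9% | 95% |
| 74 | 0.6 | 0.6 × √37 = 3.65 | 95.2% | 95% |
| 75 | 0.6 | 0.6 × √37.5 = 3.67 | 95.5% | number set |
| 60 | 0.6 | 0.6 × √30 = 3.29 | 90.3% | at least 90% |

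Inflation: 75/0.8 = 93.75, so 94 per arm and 188 in total. All of these agree with the plan.

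**2. Missing outcomes.** With 20% lost, about 75 per arm remain and power is 95.5%, provided missingness is unrelated to outcome. This covers non-adherers who are withdrawn, because nothing is collected from them afterwards.

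**3. Measured non-adherers, 0.6 SD as the average ITT effect.** They are already in the 0.6 SD. With all 94 per arm measured, noncentrality is 0.6 × √47 = 4.11 and power is 98.4%. Between no loss and 20% loss, power runs from 98.4% down to 95.5%. The claim holds.

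**4. Measured non-adherers, 0.6 SD as the effect in adherers.** Let q = 0.2 be the non-adherent share of the sleep arm, all 94 per arm measured. The mean difference is 0.6 × (1 − q(1 − r)). The last column also adds q(1 − q)(0.6(1 − r))² to the sleep-arm variance.

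| r | Mean difference (SD) | Power, SD = 1 | Power, mixture variance |
|---|---|---|---|
| 0 | 0.600 × 0.80 = 0.480 | 90.6% | 89.8% |
| 0.25 | 0.600 × 0.85 = 0.510 | 93.6% | 93.2% |
| 0.4 | 0.600 × 0.88 = 0.528 | 95.0% | 94.8% |
| 0.5 | 0.600 × 0.90 = 0.540 | 95.8% | 95.6% |
| 0.75 | 0.600 × 0.95 = 0.570 | 97.3% | not computed |

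Power reaches 95% at r of about 0.4 (0.38 to 0.43 by method). If non-adherers keep nothing (r = 0) and nobody is lost, 95% holds up to about 11–12% non-adherence.

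**5. The allowance split.** With 10% lost and 10% non-adherent, 85 per arm are measured and q = 0.1/0.9 = 0.111. On the adherer reading, r = 0 gives 0.6 × 0.889 = 0.533 SD and 93.3% (92.9% with mixture variance); r = 0.5 gives 95.7% (95.6%).

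**6. Which reading the text supports.** The sentence with 74 per arm and 0.6 SD names the ITT set. An effect used to power that set is most naturally the contrast over everyone randomised. Using 0.6 SD again for the PP set does not contradict this: if 0.6 SD is a diluted effect, it is conservative there, and a claim of at least 90% stays true.

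**The case for a change.** The best case for a change is that 10.5 never says in words whether 0.6 SD includes non-adherers, and some of its text points the other way. The halving is justified by the source study's size and its different intervention, not by adherence. The same 0.6 SD serves both the ITT and PP sets, although the two effects are equal only if people outside the PP set do not dilute the difference. Non-adherence is also named in the 20% allowance, which would be unnecessary if 0.6 SD already included it. Since withdrawal is discretionary, some non-adherers will probably be measured.

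Part of this stands. The meaning of 0.6 SD is not spelled out, and on the adherer reading the power figures in the working are correct. The rest is weaker:

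- Silence about adherence in the reasons for halving is not a statement that 0.6 SD applies to adherers only.
- Non-adherence has no allowance of its own. One 20% is shared with loss to follow-up, and the Schematic treats it as retention.
- PP membership turns on gaining an hour of sleep a night (10.4.8), not on diaries and attendance (10.4.5), so it says little about how non-adherence alters the effect.
- Values of r near zero fit poorly with people who narrowly miss an 80% target. Missing only the diary target makes someone non-compliant without implying any loss of sleep benefit.

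**Conclusion.** No change is needed. The sample-size arithmetic is right, and on the reading that 10.5 itself suggests, the power claim holds: 95.5% with 20% lost, 98.4% with nobody lost. These figures assume that missingness is unrelated to outcome.

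Power drops below 95% only if 0.6 SD is the effect in adherers, most of the 20% are non-adherers who are neither withdrawn nor lost, and they keep less than about 40% of the effect. Even at zero benefit, power is about 90%, some 4 to 5 points short. That is small beside the judgemental halving from 1.2 to 0.6 SD. The documents give no basis for choosing r, so they do not show that the design lacks its stated power.

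What remains is a missing definition that a reader can fill sensibly: 0.6 SD is the average ITT effect, non-adherers included. Stating it would leave the 188, the primary analysis and the trial's conclusions as they are. Deleting the mention of non-adherence would remove a statement that is true of non-adherers who are withdrawn.
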